11.3.2 Genetic/Genotype/Pharmacogenetic/Biomarker Assessment

Beside genetic testing for variants associated with cardiomyopathies that is mandatory, all participants will have the option to provide consent for blood to be drawn for potential future analysis of circulating biomarkers or genetic markers in relation to efficacy, safety, PD, or plasma concentration, as determined by future studies through DNA genotyping, direct sequencing, or other genetic testing modalities, unless there are local regulations prohibiting these analyses. If genetic or pharmacogenetic studies are conducted, genetic information will not be returned to participants. Pharmacogenetic samples could be used as a source of DNA for genotyping or sequencing of cardiomyopathy genes.

11.4 Safety Assessments

Safety will be assessed throughout the study as indicated in APPENDIX 1. Safety assessments include medical history, physical examinations, as determined by TTE, triplicate 12-lead ECGs, vital signs, observed and participant-reported AEs, serum troponin concentrations, and safety laboratory tests.

The Sponsor will closely monitor safety on an ongoing basis.

Any abnormal findings judged by the Investigator to be clinically important (new or worsened from Baseline) will be recorded as an AE which will be reviewed by the Sponsor.

11.4.1 Medical History

A complete medical history will be recorded at the Screening visit, which will include evaluation (past or present) of the cardiovascular and heart failure medical history as well as the following: general, head and neck, eyes, ears, nose, throat, chest/respiratory, gastrointestinal/liver, gynecological/urogenital, musculoskeletal/extremities, skin, neurological/psychiatric, endocrine/metabolic, hematologic/lymphatic, allergies/drug sensitivities, past surgeries, substance abuse, or any other diseases or disorders as well as participation in clinical studies (study drug and/or device or other therapy).

11.4.2 Vital Signs

Vital signs will be assessed throughout the study as indicated in APPENDIX 1 and will include temperature, HR, and blood pressure (BP). HR and BP shall be the mean of 3 measurements taken with the participant in a supine position after resting for at least 5 minutes.

11.4.3 Physical Examination

Height (cm) and weight (kg) will be measured at Screening and timepoints indicated in APPENDIX 1.

A complete physical examination will be conducted including a neurological examination (gross motor and deep tendon reflexes), and assessment of the following: general appearance, skin, head and neck, mouth, lymph nodes, thyroid, abdomen, musculoskeletal, cardiovascular, neurological,

and respiratory systems. At all other timepoints, an abbreviated physical examination (pulmonary, cardiac, abdominal, and other systems related to symptoms) will be conducted.

11.4.4 Electrocardiograms (12-Lead ECG)

The triplicate 12-lead ECG should be obtained as indicated in APPENDIX 1. The Investigator may add extra 12-lead ECG assessments if there are any abnormal findings or if the Investigator considers it is required for any other safety reason. If the participant has a new troponin abnormality (Section 11.4.6) or any signs or symptoms suggestive of possible cardiac ischemia, additional ECGs should be obtained. These assessments should be recorded as unscheduled assessments. All study ECGs will be read locally and sent to an ECG core laboratory.

The Investigator will judge the overall interpretation as (a) normal, (b) abnormal without clinical significance, or (c) abnormal with clinical significance. If clinically significant, the abnormality will be recorded. In addition, at each visit, the Investigator or sub-investigator should compare the available ECGs at the visit to those from the prior visit. If there are signs of ischemia, dosing should be withheld until there is full understanding of the possible ischemic changes.

In addition, at Visit 3A and Visits in Part B, the Investigator should evaluate the triplicate 12-lead ECGs and confirm lack of QTcF prolongation (Section 6.2) to continue treatment with study drug. The Investigator will review the ECG and correlate abnormal findings with any other clinical findings, participant's medical history, and laboratory data to determine the clinical importance of the finding.

11.4.5 Extended Cardiac Rhythm Monitoring

Part A: If using historical LVEF to qualify a participant, a cardiac rhythm monitoring patch will be placed at the first Screening visit (Visit 1.1A). If using 2 Screening TTEs, the patch will be placed at the time of the second Screening visit (Visit 1.2A). A new patch will be placed at the start of Treatment Period 1, after dosing.

Part B: A cardiac rhythm monitoring patch will be placed at Visits 1B, 6B, 8B, 10B, and EOT.

The duration of monitoring will range from 5-14 days. If the patch becomes detached prior to 5 days, a new patch should be placed as soon as possible. Once the patch detaches (after at least 5 days), participants will be instructed to mail the patch back to the site.

11.4.6 Troponin Levels

In Part A, hsTnT, TnI, and hsTnI samples will be collected at timepoints as indicated in APPENDIX 1. Samples will be analyzed at a central laboratory at all clinic visits after Part A Screening (Visits 1.1A to Visit 5A). There are no discontinuation criteria related to troponin levels in Part A.

In Part B, TnI (standard and high-sensitivity) and hsTnT samples will be collected as described in APPENDIX 1 and analyzed by the central laboratory.

In Part B, troponin increase will be defined as:

1) If TnI (standard) level is below ULN at Baseline (value obtained at Visit 1B) and subsequently increases to more than 0.05 ng/mL on any assay after start of dosing

2) If the TnI (standard) level is above the ULN at Baseline and then subsequently rises by more than 0.05 ng/mL above the participant's Baseline value (obtained at Visit 1B) on any assay after start of dosing.

If either of these conditions are met from start of Visit 1B to Visit 6B (week 24) and the absolute TnI (standard) level is below 0.1 ng/mL, the totality of the clinical data will be reviewed by the Coordinating Investigator, the consulting Safety Reviewer, and the Sponsor's Medical Monitor periodically to determine if any signs of ischemia are seen. During this time, the participant will continue to take danicamtiv at the same dose. Subsequent telehealth visits will be transitioned to in-person clinic visits with 12-lead ECGs and troponin tests until troponin levels are stable or declining.

If the TnI (standard) level exceeds 0.1 ng/mL, at any time, the participant will be asked to return for repeat evaluation as soon as possible. If this level of TnI (standard) is confirmed, treatment with danicamtiv will be temporarily discontinued and an ad hoc review by the Coordinating Investigator, the consulting Safety Reviewer, and the Sponsor's Medical Monitor will be triggered.

Abnormal and/or rising troponin values (as per Investigator's judgment and considering potential Baseline troponin elevation frequently observed in heart failure) should lead to the participant being clinically evaluated for possible myocardial ischemia. Also, if the participant has any signs or symptoms suggestive of possible cardiac ischemia, additional serial troponin (and other safety labs, including CK-MB samples) should be obtained and subsequent dosing should be withheld until there is full understanding of the possible ischemic event. The Investigator will evaluate the entire clinical context (eg, signs, symptoms, new ECG changes, new troponin, and CK–MB abnormalities) and correlate with any other relevant clinical findings, participant's medical history, and laboratory data to determine the clinical significance of the findings.

If the Investigator assessment is that an AE has occurred, the event should also be reported as an AE accordingly (Section 12).

11.4.7 Adverse Events

Please see Section 12 for information on evaluating, recording, and reporting AEs.

11.4.8 Safety Laboratory Tests (Other Than Troponin)

Samples will be drawn for safety laboratory tests at the timepoints indicated in APPENDIX 1. At Screening, assessments will be made by the central laboratory. If the Investigator has any questions regarding eligibility, the Sponsor should be contacted.

Screening laboratory testing will include thyroid-stimulating hormone (TSH) and iron (Fe)/total iron-binding capacity (TIBC)/ferritin to exclude uncontrolled thyroid functions and Fe overload.

11.5 Missed Evaluations

Evaluations should occur within the assessment window specified by the protocol. If an evaluation is missed, it should be performed as close as possible to the original time.

11.6 Participant Restrictions During the Study

Starting at Screening and throughout the study, participants should be instructed to maintain a stable lifestyle. This includes but is not limited to:

- Concomitant medications: every effort should be taken to maintain stable doses of concomitant medications, and to take such medications at consistent times during the day; for cardiovascular drugs, this will allow to minimize variability in cardiac loading conditions.
- Activity levels:
 - In Part A, from 72 hours prior to the first dose through the Follow-up visit, participants should not engage in unaccustomed intensive exercise.
 - In Part B, participants should follow their customary exercise regimen and not engage in unaccustomed intensive exercise. Any planned increase in the amount of regular physical exercise should be discussed with the Investigator prior to commencing.
- Meals/food:
 - Abstain from grapefruit or grapefruit juice, Seville oranges, and quinine (eg, tonic water).
- Fluid intake: maintain usual daily fluid intake and avoid excessive alcohol consumption.

In addition, starting at Screening, participants will be required to abstain from blood or plasma donation until 3 months after the final study visit.

Contraception requirements are discussed in Section 10.2.

If participants are participating in Part B observational study, this restriction will not apply.

12 EVALUATION, RECORDING, AND REPORTING OF ADVERSE EVENTS

12.1 Definitions

12.1.1 Adverse Event

An AE is any untoward medical occurrence, or the deterioration of a preexisting medical condition (other than the condition that is being treated by the study) associated with the use of a study drug in humans, whether or not it is considered related to the study drug. An AE (also referred to as an adverse experience) can, therefore, be any unfavorable and unintended sign (eg, tachycardia, enlarged liver, clinically important abnormal laboratory result or diagnostic procedure), participant-reported symptom (eg, nausea, chest pain), or evidence of any disease activity temporally associated with the use of a study drug, whether or not related to the study drug.

In clinical studies, an AE can include an undesirable medical condition occurring at any time after the participant has signed informed consent, including run-in or washout periods, even if no specific treatment has been administered.

Preexisting medical conditions (other than natural progression of the disease being studied) judged by the Investigator or participant to have worsened in severity or frequency or changed in character during the protocol-specified AE reporting period will be reported as AEs or SAEs as appropriate.

Imaging-based assessments of decrease in contractility are not considered AEs unless associated with symptoms or signs of clinical concern on the part of the Investigator. Such events should be categorized as an AE defined in terms of those symptoms or signs.

An AE or SAE can also be a complication that occurs as a result of protocol-mandated procedures (eg, procedures such as blood draws).

For the Sponsor to collect additional information about clinically important laboratory results or diagnostic tests (eg, blood, ECG, imaging), at a minimum, the following abnormalities should be captured on the AE eCRF:

- Any test result that meets the definition of an AE.
- Any clinically important test abnormality that suggests a disease and/or organ toxicity that has worsened or is new (eg, > 3 times deviation from the upper or lower limit of the analyzing laboratory reference range, or as otherwise specified in the protocol).
- Any test abnormality that requires the participant to have study drug discontinued or interrupted or in the clinical judgment of the Investigator.
- Any test abnormality that requires the participant to receive specific corrective therapy, close observation, more frequent follow-up assessment, or further diagnostic investigation.

The term AE is used generally to include any AE whether serious or nonserious.

12.1.2 Serious Adverse Events

An SAE is an AE that fulfills one or more of the following criteria:

- Results in death
- Is immediately life-threatening (places the participant at immediate risk of death from the event as it occurred)
- Requires in-participant hospitalization or prolongation of existing hospitalization
- Results in persistent or significant disability or incapacity or substantial disruption of the ability to conduct normal life functions
- Results in a congenital abnormality or birth defect
- Is an important medical event that may not result in death, be life-threatening, or require hospitalization, but may be considered an SAE when, based upon appropriate medical judgment, it may require medical or surgical intervention to prevent 1 of the outcomes listed above

12.1.3 Adverse Events of Special Interest

Overdose (asymptomatic and symptomatic) and increased troponin are considered AESI; AESIs are required to be reported by the Investigator to the Sponsor within 24 hours, irrespective of regulatory seriousness criteria.

Increased troponin will be captured as an AESI under the following conditions: if the participant's TnI (standard) level reaches a level greater than 0.1 ng/mL on any assay after the start of dosing.

12.2 Events NOT Meeting the Definition of an Adverse Event

If an event is not an AE, then it cannot be an SAE, even if the event outcome meets the definition for seriousness defined by the criteria in Section 12.1.2. Instances where an event is not an AE include:

- Medical or surgical procedure (eg, endoscopy, appendectomy): the condition that leads to the procedure is the AE.
- Situations in which an untoward medical occurrence did not occur (social and/or hospital admission/extension for convenience).
- The disease/disorder being studied or expected progression, signs, or symptoms of the disease/disorder being studied, unless more severe than expected for the participant's condition.
- Anticipated day-to-day fluctuations of preexisting disease(s) or condition(s) that are present or detected at the start of the study that do not worsen.
- Hospitalization for a preexisting condition, provided all of the following criteria are met:
 - The participant has not experienced an adverse event.
 - The hospitalization was planned prior to the study or was scheduled during the study when elective surgery or procedure became necessary because of the expected normal progression of the disease.

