13.2 Study Endpoints

13.2.1 Primary Endpoint

Primary endpoints are clinical safety and tolerability as assessed by the following:

- Frequency of AEs and SAEs in Part A
- Frequency of clinically significant abnormalities from vital signs, AEs, physical examination, ECG recordings, and safety labs in Part A

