- ^u Triplicate 12-lead ECG obtained at Visit 3A will be reviewed by the Investigator to confirm lack of QTcF prolongation in order to continue with study drug treatment (Section 6.2) before being sent to the ECG core laboratory.
- ^v Changes in baseline conditions from once the ICF is signed will be recorded as an AE. All changes, unless otherwise specified, that occur after the administration of study drug will be considered treatment emergent AEs.
- ^w FSH level assessment done at Screening is only for women of non-childbearing potential.
- ^x Should be done before any other assessments.
- ^y If rescreening is conducted, repeat of genetic testing at Screening is not necessary. Up to 1 rescreen per participant is permitted.

Table 4:Schedule of Assessments, Part B (Active Cohort)

	End of Part A					Part B,	Year 1					
Visit Day	14 days + 7d after V4A	Day -28 to -1 (Rescreening, if needed)	Day 1 (Baseline)	Week 2	Week 6	Week 12	Week 18	Week 24	Week 30	Week 36	Week 42	Week 48
Visit Number	V5A ^a	V0B ¹	V1B ^a	V2B	V3B	V4B	V5B	V6B	TH1B	V7B	TH2B	V8B
Visit Windows		-28 days		±2 days	±7 days	±7 days	±7 days	±7 days	±7 days	±7 days	±7 days	±7 days
Telehealth Visit									X		X	
Informed Consent		Х	X (if needed)									
Medical History		Х	X (if needed)									
Vital Signs		Х	Х	Х	Х	Х	Х	Х	Xi	Х	Xi	Х
Weight		Х	Х	Х	Х	Х		Х				Х
Complete Physical Exam		Х										
Symptom-directed Physical Exam			Х	Х	Х	Х	Х	Х		Х		Х
TTE			X ^d	X ^{c,e}	X ^{c,e}	X°		X°				X°
12-lead ECG	Х	Х	Х	Х	Х	Х	Х	Х	Xi	Х	Xi	Х
Cardiac Rhythm Monitoring ^f			Х					Х				Х
Activity Monitor ^g			Х					Х				Х
CMR ^h			X ^d									Х
6MWD (in clinic)			X ^d					Х				Х
NYHA Functional Classification	Х		Х		Х	Х	Х	Х		Х		Х
KCCQ-23	Х		Х		Х	Х	Х	Х	Х	Х	Х	Х
hsTnT/TnI/hs-TnI (Central) ^b	Х		Х	Xj	Xj	Xj	Xj	Xj	Xj	Х	Xj	Х

Table 4:Schedule of Assessments, Part B (A	Active Cohort)
--	----------------

	End of Part A					Part B,	Year 1					
Visit Day	14 days + 7d after V4A	Day -28 to -1 (Rescreening, if needed)	Day 1 (Baseline)	Week 2	Week 6	Week 12	Week 18	Week 24	Week 30	Week 36	Week 42	Week 48
Visit Number	V5A ^a	V0B ¹	V1B ^a	V2B	V3B	V4B	V5B	V6B	TH1B	V7B	TH2B	V8B
Visit Windows		-28 days		±2 days	±7 days	±7 days	±7 days	±7 days	±7 days	±7 days	±7 days	±7 days
Telehealth Visit									Х		X	
NT-proBNP (Central)	Х		Х	Х	Х	Х	Х	Х	Xj	Х	Xj	Х
Chemistry, Hematology (Central)	Х	X°	Х	Х	Х	Х	Х	Х		Х		X
Pregnancy Test ^k	Х	Х						Х				Х
Danicamtiv Plasma PK Sample			X (pre- dose_	Xc	Xc	Xc	Х	Xc		Х		Xc

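### Sections 12.1.1 and 12.2 keep expected progression of the studied disease out of AEs and SAEs while 11.4, 12.3 and the schedule footnotes do not, so heart-failure events can be counted inconsistently

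*Combined protocol and SAP*

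**What the plan says.** **Text that excludes.** Section 12.1.1 counts deterioration of a preexisting condition as an AE, but with the qualifier "other than the condition that is being treated by the study". A later paragraph of the same section sends worsening to the AE form for "Preexisting medical conditions (other than natural progression of the disease being studied) judged by the Investigator or participant to have worsened", so natural progression is excepted again. Section 12.2 lists among non-AEs "The disease/disorder being studied or expected progression, signs, or symptoms of the disease/disorder being studied, unless more severe than expected", with the participant's own condition as the yardstick. It also states: "If an event is not an AE, then it cannot be an SAE, even if the event outcome meets the definition for seriousness".

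**Text that includes.** Section 11.4 has any clinically important abnormal finding that is new or worse than Baseline recorded as an AE. Section 12.3 has preexisting conditions that become more severe after the first dose reported as AEs, with no exception for the studied disease. Footnote v to the Part A schedule reads "Changes in baseline conditions from once the ICF is signed will be recorded as an AE", and footnote m to the Part B active-cohort schedule says the same.

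**What is counted.** The first primary endpoint in Section 13.2.1 is "Frequency of AEs and SAEs in Part A". The second is the frequency of clinically significant abnormalities on vital signs, examination, ECG and laboratory tests. Section 13.2.3 repeats the pair for Part B as exploratory endpoints, using treatment-emergent AEs and SAEs.

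**The concern.** The studied disease is dilated cardiomyopathy with LVEF of 15 to 45%, so its progression includes worsening heart failure. That is also one form that harm from a drug acting directly on the myocardium could take. In a single patient with no concurrent control, expected progression cannot be told apart from drug harm. The classification is left to an unmasked investigator, without criteria or adjudication. The Part B observational cohort does not help, because it consists of participants who did not opt for treatment.

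The safety frequencies thus depend on which section a site follows and on how it reads the word expected. The likely direction of error is downward, for the events most relevant to the safety question. The 24-hour reporting rule in Section 12.3 is also affected: it is tied to SAEs and AESIs, and Section 12.1.3 limits AESIs to overdose and raised troponin.

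**Working it through.** The plan gives no event rate or power figure on this point, and Section 13.1 calls the sample size empirical, so there is no figure to reproduce. The check is a reading of the rules on concrete cases, followed by simple arithmetic on scale.

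**1. An unplanned heart-failure admission in Part B, under each set of rules.**

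| Question | Following 12.1.1 and 12.2 | Following 12.3 and footnote m |
|---|---|---|
| Is the worsening an AE? | No, if judged expected for that participant | Yes: a preexisting condition has become more severe |
| Is the admission an SAE? | No, because a non-AE cannot be one | Yes: hospitalisation is a 12.1.2 criterion |
| 24-hour report? | Not triggered | Triggered |
| In the 13.2.3 frequency? | No | Yes |

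The separate hospitalisation bullet in 12.2 covers only planned or elective admissions in a participant without an AE. An unplanned admission can therefore be excluded only through the disease-progression bullet.

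**2. A death.** Section 12.3 names deaths next to new SAEs as reportable, so a death should reach the sponsor. Section 12.3.1.1 treats death as an outcome rather than an event name, so it enters an AE table through its cause. If that cause is classed as expected progression, the death can be missing from the SAE frequency.

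**3. Is the event counted elsewhere?** Section 13.2 has no endpoint for heart-failure worsening, hospitalisation or death. The second primary endpoint and the echocardiographic endpoints cover findings and measurements, not clinical events. Section 12.1.1 also keeps an imaging-only fall in contractility out of AEs unless symptoms or signs of concern accompany it.

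**4. Size of one omission.** Inputs: planned completers of about 12 (MYH7), 12 (TTN) and 16 (other), 40 in all (Section 13.1). Effect of one omitted participant-level event = 100/n percentage points. The exact (Clopper-Pearson) 95% intervals show what a reader would see with and without it; the counts of 0 and 1 are assumptions.

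| n | 100/n | 0 events reported | 1 event reported |
|---|---|---|---|
| 12 | 8.3 points | 0 to 26.5% | 0.2 to 38.5% |
| 16 | 6.3 points | 0 to 20.6% | 0.2 to 30.2% |
| 40 | 2.5 points | 0 to 8.8% | 0.1 to 13.2% |

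**5. Where it matters more.** Part A treatment lasts 9 to 16 days (Section 6.3). Adding the 14-day treatment-emergent window (Section 13.3.7) gives at most 16 + 14 = 30 days. Part B treatment runs to Week 96, that is 96 × 7 = 672 days, or 672/16 = 42 times the longest Part A treatment. The opportunity for misclassification therefore lies mostly in Part B.

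**The case against.** The strongest reply is that the plan does not lose these events. Section 12.3 and the footnotes require recording. Section 12.1.1 itself includes evidence of disease activity that coincides in time with study drug. It also makes a contractility decrease with symptoms an AE, and it sends clinically important test abnormalities to the AE form. The exception in 12.2 is judged per participant, and participants enter stable, on stable heart-failure medication, with no heart-failure admission in the previous 90 days. An unplanned admission or death in such a person would be hard to call no worse than expected. LVEF, NYHA class, KCCQ-23 and NT-proBNP are collected in any case, the analysis is descriptive, and Section 13.3 leaves full detail to a SAP.

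Much of this stands. A reader might infer from 12.2 alone that heart-failure worsening, admissions and deaths judged expected simply vanish from the safety data. The documents do not support that, because other sections point to recording and deaths are reportable in their own right. A reader might also size the problem from the five-year mortality in the Introduction. That figure is for heart failure patients in general and says nothing about how many events would be misclassified.

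The reply does not remove the conflict. It could be said that 12.2 is the specific rule and governs the general ones. However, 11.4 and 12.3 do not refer to it, and the qualifier in footnotes v and m attaches to the treatment-emergent label, not to the instruction to record. If 12.2 does govern, the under-count is built in. If it does not, the rule is misleading. A SAP can add tables, but it cannot by itself restore events that sites did not record.

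**Conclusion.** The concern holds as an internal contradiction combined with an undefined judgement. The AE and SAE frequencies, primary in Part A and exploratory in Part B, do not have one event definition for worsening of the studied disease, and they can be biased downward. That bias is possible rather than demonstrated: the documents allow no estimate of how many events would be affected.

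Each omission is worth 8.3, 6.3 or 2.5 points at n = 12, 16 or 40. This assumes that the planned completer numbers are the denominators and that the participant has no other event in the same tabulated category. Part B is optional with no target size, so its denominators may be smaller and each event would then weigh more. The practical effect is probably small in Part A and larger in Part B, if heart-failure events accrue roughly with time on study. This should be fixed, but it does not undermine the design.

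**What to change.** Reconcile 12.1.1 and 12.2 with 11.4, 12.3 and footnotes v and m. State once that new or worsened heart failure, unplanned cardiovascular hospitalisation and death after consent are recorded as AEs, and as SAEs when a 12.1.2 criterion is met, whether or not the investigator judges them expected. Amend the two exceptions in 12.1.1 and the progression bullet in 12.2 to match.

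In 13.2 and 13.3.7, add separate tabulations of heart-failure worsening, unplanned cardiovascular hospitalisation and death, by Part and cohort.

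The cost is a wording change, site retraining, a few more AE and SAE reports, and slightly higher reported rates. This is a change to recording and tabulation only. Because Section 6.2.2 refers to drug-related SAEs, the sponsor should check how the revised recording rule reads alongside it; this point takes no position on that rule.
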